## Study Statistics

Measures/ Data Analysis D.3.1 Measures F CG outcome measures will be collected at baseline, 14, 30, 60, 90, and 120 days. The collection schedule reflects that meetings are required to be held every 14 days and our desire to have a measure close to the patient's death without unduly burdening FCGs. Our experience showed that 75% of FCGs were no longer in the study after 90 days due to the death of their patient. Research Specialists will conduct phone interviews with all FCGs 14-21 days after their patient's death. Using a convenience sample of hospice staff an annual electronic survey will be distributed annually. Research specialists will perform all data collection using RedCap and/or the phone.

**Hypothesis 1 (H1)** FCG participating in both intervention groups will report lower levels of anxiety, increased levels of pain knowledge, increased perceptions of involvement in care, increased communication, decreased depression, increased quality of life, and lower patient pain compared to enhanced usual care.

**Hypothesis 2:** FCGs participating in SDM process in team meeting will report lower levels of anxiety, increased levels of pain knowledge, and lower patient pain compared to either the Facebook group or usual care group.

**H3** The effect of the ACCESS intervention compared with the usual care will be greater for those with worse anxiety scores at baseline.

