A CCXOPRCT design initially randomly assigns hospice sites to two of three groups: 1) Group 1 participants will serve as the control and receive usual hospice care enhanced by hospice staff training in shared decision making, 2) Group 2 participants will receive enhanced usual care as well as participate in a private Facebook support group to increase their knowledge and provide social/emotional support, 3) Group 3 participants will receive enhanced usual care, participate in the Facebook support group, and participate in hospice team meetings with a shared decision making process. After 12 months the group goes through a 90 day (or less if all have completed the trial earlier) washout period so all participants can complete the study. The group then is assigned to a second arm of the study for another 12 months. Again following a washout period so all participants complete the trial and then re-assignment to their first study arm again. Each cluster will go through two arms of the intervention, although participants will only complete one arm. A schedule has been developed. We will use qualitative and quantitative methods in parallel and equal status to measure the efficacy of the intervention.

**Our overall hypothesis is that ACCESS will improve hospice cancer family caregiver knowledge and emotional state (via Facebook), thereby facilitating a shared decision making process, which will result in improved caregiver anxiety and knowledge and improved pain control for patients.**

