## Randomization

We will use a cluster randomization design because:

1. Our aims contain individual level and organizational level outcomes. Study aim 3 can then be assessed at the organizational level as well as the individual level.
2. Given the large geographic distance covered by the six participating hospice sites, it is far more cost effective to focus our intervention costs at specific hospice sites rather than across all sites. This will allow us to assess the total impact of an agency wide intervention. In keeping with the pragmatic goal of our trial this is more reflective of how implementation would actually be done at a hospice site, as individuals would not be given random interventions in real life.
3. We will avoid the contamination between the intervention groups and the control group- an unavoidable consequence of having both groups in one hospice site. We believe contamination may have lowered our ability in the pilot study to detect the change in the primary outcome.
4. These sites provide us with a diverse sample. We will have rural and urban hospice programs, a greater number of under represented minorities, and a more diverse hospice staff.

We have chosen a cross over design to increase precision as each arm of the study may serve as its own control group, thus reducing the number of participants necessary to have adequate power. This has been the recommended design for small numbers of clusters that are not meeting recruitment goals.

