#### **RQ4: What are the perceptions and satisfaction of FCGs and staff with both intervention groups.**

Measures:

Leeds Attitude Concordance II

Perceived Involvement in Care Scale

FCG Interviews

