### Qualitative Data

Video-recording: We will record 100% of all care plan meeting days with the web- conferencing intervention participants and 100% of meetings where all group participants are discussed for comparison using qualitative analysis until June 10, 2020 Facebook posts: We will also maintain 100% of the Facebook conversations for analysis and track all “likes” noted on posts. FCG Interviews: We will interview 100% of all FCGs in each group (total of 642 interviews) 14-21 days following their patient’s death. The interviews will be semi-structured based on guides developed in our preliminary work (see Appendix) and will include a post GAD-7 measure to evaluate post-care stress. Staff surveys: convenience sample annually by REDCap and distributed through the hospice sites email using the LEED questionnaire.

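### The yearly staff survey is not tied to the crossover periods, so staff answer after uneven exposure to each arm

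*Combined protocol and SAP*

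**What the plan says.** Two places set the staff survey's timing. Study Statistics (D.3.1 Measures) states: "Using a convenience sample of hospice staff an annual electronic survey will be distributed annually". Qualitative Data repeats it: "Staff surveys: convenience sample annually by REDCap", using the Leeds questionnaire. Neither gives a calendar date or a point within an arm period.

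The Abstract sets out the crossover that each site follows. The first period ends as follows: "After 12 months the group goes through a 90 day (or less if all have completed the trial earlier) washout period". For the next step the text reads: "The group then is assigned to a second arm of the study for another 12 months". The sequence closes with a second washout and a return to the arm that the site began with, and the length of that last period is not stated. A crossover schedule is said to exist, but its content is not given.

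The survey serves three purposes. Aim 3 concerns how satisfied staff and caregivers are with shared decision making (SDM), and the Randomization section adds: "Study aim 3 can then be assessed at the organizational level as well as the individual level". RQ4 asks: "What are the perceptions and satisfaction of FCGs and staff with both intervention groups", and lists the Leeds measure. RQ1 also lists the annual staff survey.

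The staff items named in the List of Staff Measures include site but not arm or period. That list points to a REDCap attachment which is not among the documents. No section gives a quantitative analysis of the staff scores or a rule for responses received in a washout.

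**The concern.** A survey every 12 months suits a parallel cluster design with one arm per site, which Study Procedures still describes. Against a cycle of up to 15 months it moves relative to the arm periods. It may reach staff late in an arm, in a washout, or just after a switch.

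This matters more for staff than for caregivers. Each caregiver completes one arm, but staff who stay at a site work through both. Early in a new arm few caregivers will have been enrolled. A Leeds score labelled Group 3 could then come from staff who have seen very few SDM meetings, and a Group 1 score from staff who have only just stopped holding them. The label would be right but the experience behind it thin.

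The second arm is the exposed point, because each site runs it once and then goes back to its first arm. With six participating sites there are at most six second-arm site-periods, shared among the arms. A few badly timed surveys could therefore colour an organizational-level summary.

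**Working it through.** The documents give no sample size, power or other figure for the staff survey, so there is none to reproduce. The check is timeline arithmetic.

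**Inputs**
- Survey interval: 12 months (Study Statistics; Qualitative Data).
- First and second arm periods: 12 months each (Abstract).
- Washout *w*: up to 90 days, about 3 months, and possibly shorter (Abstract). Values of 0, 1, 2 and 3 months are used.
- Assumptions: third period of 12 months (its length is not stated), strict 12-month survey spacing, equal washouts within a site.

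**Timeline of one site, in months from its start**
- First arm: 0 to 12
- Washout 1: 12 to 12 + *w*
- Second arm: 12 + *w* to 24 + *w*
- Washout 2: 24 + *w* to 24 + 2*w*
- First arm again: 24 + 2*w* to 36 + 2*w*

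Surveys fall at *s*, *s* + 12, *s* + 24 and so on. The offset *s* of the first survey lies anywhere from 0 to 12 and is treated as equally likely throughout.

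**Cycle length.** 12 months + up to 3 months = up to about 15 months.

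**Coverage.** A 12-month window always holds exactly one point of a 12-month grid. Every arm period therefore gets one survey, whatever *s* and *w* are.

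**Time in the arm at survey.** While no survey falls in a washout, the times are *s*, *s* − *w* and *s* − 2*w*. With *w* = 3 and *s* = 9 they are 9, 6 and 3 months, so each is 3 months earlier than the last. When a survey does fall in a washout, the next one comes late in its period. With *w* = 3 and *s* = 4:
- month 4 is 4 months into the first arm;
- month 16 is 16 − 15 = 1 month into the second arm;
- month 28 is in washout 2 (27 to 30);
- month 40 is 40 − 30 = 10 months into the third period.

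**A survey in a washout.** Washout 1 is hit when *s* is in 0 to *w*, and washout 2 when *s* is in *w* to 2*w*. The share of offsets is 2*w*/12.

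**Second arm surveyed early.** Its survey falls in its first 3 months when *s* + 12 lies between 12 + *w* and 15 + *w*, so *s* is in *w* to *w* + 3. The share is 3/12 = 25% for every *w* from 0 to 3. For the first month alone it is 1/12 = 8%.

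**Overlap.** Within that early range, offsets from *w* to 2*w* also put a survey in washout 2, just after a full 12 months of the second arm. The share with an early in-arm survey and no such follow-up is (3 − *w*)/12.

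| Washout (months) | Some survey in a washout | Second arm's in-arm survey in its first 3 months | Same, and no survey in washout 2 |
|---|---|---|---|
| 0 | 0% | 25% | 25% |
| 1 | 17% | 25% | 17% |
| 2 | 33% | 25% | 8% |
| 3 | 50% | 25% | 0% |

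All columns are shares of all offsets.

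**The case against.** A reader might infer that the survey cannot give staff satisfaction by arm, or that arms would be mixed. The documents do not support that. Every arm period is surveyed once, site is recorded, arm is set by site, and a schedule exists, so site, date and schedule identify the arm. The unseen attachment may also record the arm directly, so a missing arm variable cannot be asserted.

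A reader might also count every washout survey as lost. The Abstract describes the washout as time for enrolled caregivers to finish, so staff may still be serving the outgoing arm after a full year of it. Such a response can be attributed to that arm or set aside, and it is extra to the in-arm surveys. With full washouts it even supplies a well-exposed second-arm reading whenever the in-arm one was early. This helps only if the plan says how washout responses are attributed, and it does not.

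The 50% is the upper end, since washouts may be shorter than 90 days. Some offsets give ample exposure: surveys at months 12, 24 and 36 follow 12, 9 and 6 months in the arm just finished or current.

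Nor does Aim 3 as worded ask for a comparison by arm; only RQ4 refers to the intervention groups. H1 to H3 concern caregivers, and the staff survey is a convenience sample placed under Qualitative Data. Finally, a yearly interval does not forbid a fixed point in each period.

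These points limit the finding but do not remove it. Correct labelling does not make up for lack of exposure, and the 25% figure for the second arm holds at every washout length considered.

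**Conclusion.** The concern holds as a weakness of timing. The yearly survey is not anchored to the arm periods, so staff exposure at survey is left to chance. With full washouts the survey moves about 3 months earlier per period, and half of the offsets put one survey in a washout. At any washout from 0 to 3 months, a quarter of offsets place the second arm's only in-arm survey in its first 3 months. These shares rest on strict 12-month spacing, equal washouts, a 12-month third period and evenly spread offsets.

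The effect is to weaken the RQ4 comparison of staff satisfaction and the organizational-level assessment of Aim 3, without preventing either. The primary GAD-7 analysis is untouched. This is a cheap improvement to a secondary descriptive measure.

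**What to change.** In Study Statistics and Qualitative Data, replace the yearly interval with one staff survey per site in the last month of each arm period, before the washout. Record on each response the site's current arm, the period, and any earlier arms the respondent worked under. Summarise Leeds scores by arm period within site. State the length of the third period and how replies that arrive during a washout are attributed.

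The cost is protocol wording and changed REDCap send dates. With full washouts a site's sequence lasts 36 + 2 × 3 = 42 months and needs three surveys. A yearly survey over the same 42 months gives three or four (42/12 = 3.5), so there are no extra surveys and no extra $30 staff payments.

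The downside is that sites are surveyed on their own switch dates, not on one common date. The change also leaves carry-over: staff who practised SDM in one period bring that experience to any later survey. That comes from crossing sites over and should be acknowledged when the results are reported.

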## QUANTITATIVE AND QUALITATIVE MEASURES

**LIST OF FAMILY CAREGIVER MEASURES** (see REDCap survey attachments for specific questions/measures used):

**Demographics**- basic demographic information about the family caregiver, patient diagnoses, medication administration

**GAD-7 Generalized Anxiety Disorder**- primary outcome measuring anxiety

**Family Pain Questionnaire**- secondary outcome measuring family pain knowledge

**Perceived Involvement in Care Scale**- secondary outcome measuring involvement in patient's care and management of the illness in cooperation with the hospice staff

**CCQ Care Giver Communication Questionnaire**- secondary outcome measuring hospice and caregiver communication and hospice support

**PHQ 9 Public Health Questionnaire**- secondary outcome measuring depression

**SF12 General Health**- secondary outcome measuring family caregiver health

**CQLI-revised Caregiver Quality of Life**- secondary outcome measuring family caregiver quality of life

**Edmonton Symptom Assessment**- secondary outcome measuring patient symptoms, including pain

**Zarit Burden Inventory**- secondary outcome measuring personal and role strain of family caregiver

**Facebook Survey Items**- (Group 2 and 3 only) measures family caregiver response to Facebook educational topics

#### **LIST OF STAFF MEASURES** (see REDCap staff survey attachment for specific items/questions)

**Staff Demographics**- basic information including job title, site, number of years in hospice, number of years at the specific hospice site

**Leeds Concordance of Care II- revised**- measures hospice staff satisfaction with involvement of patients and family caregivers in treatment planning and shared decision-making

### **RESEARCH QUESTION MEASURES**

#### **RQ1 In what ways do roles of team members change when FCGs are in team meeting?**

Measures:

Video recordings of team meetings

Annual Staff survey

#### **RQ2 In what ways does Facebook affect FCG information and emotional state for SDM for intervention groups?**

Measures:

Facebook group postings

Family Pain Questionnaire

Facebook Survey Items

#### **RQ3 What are the barriers and facilitators for SDM in the team meeting?**

Measures:

Video recordings of team meetings

Care Giver Communication Questionnaire

#### **RQ4: What are the perceptions and satisfaction of FCGs and staff with both intervention groups.**

Measures:

Leeds Attitude Concordance II

Perceived Involvement in Care Scale

FCG Interviews

## Statistical Analysis

Statistical Assumptions: We will routinely test assumptions of linearity, independence and homoscedasticity by calculating and plotting residuals and Cook's distance for all models. Where data are missing, we will substitute the mode for categorical data and the median for continuous data, given that <0.5% of data were missing for any measure in our preliminary trial. If the proportion of missing data is higher, we will use multiple imputation. We use the final measure provided by caregiver before patient death in the analysis. Because individuals are randomly allocated and the sample size is relatively large, we expect that both known and unknown confounders will be distributed evenly among the three groups. Because randomization will be stratified by hospice, equivalent proportions from each hospice will be allocated to each group. However, we will test for an interaction effect between study group and hospice to assess whether the effect of the intervention differs between hospices. This will be tested by introducing a Study Group X Hospice interaction term into each of the regression models discussed below. We acknowledge that this study is not powered to detect small interaction effects. Additional confounders will only be introduced as covariates if we find evidence of imbalance between groups at baseline.

We will test whether randomization created balanced groups by comparing baseline measures and demographic characteristics, using chi-square or t-test analysis for categorical or continuous variables, respectively. Variables that differ significantly between groups will be included in regression models as potential confounders. To compare outcomes for Hypotheses 1-4 (H1-H4), we will use the last available measure post-baseline and prior to death or the end of the study. The last available measurement typically represents the FCG's measure at the last point prior to the patient's death. This is a last observation analysis. Carpenter and Kenward argue that, in such analyses, time to this event should be taken into account. We will therefore include time from study enrollment to the last observation as a covariate. We will report estimates with 95% confidence intervals. To draw inferences from our study to the likely benefit to an equivalent population where the intervention under trial is a model of service delivery, all analyses of outcomes will be by intention-to-treat. The intention-to-treat analysis, consistent with the objectives of a pragmatic trial, will minimize the influence of "informative missingness" of the data and preserve groups' comparability.

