## **Study Procedures**

We propose an intervention to target education and emotional support to FCGs based on a structured process for SDM. ACCESS (Access for Cancer Caregivers to Education and Support for Shared decision- making) has three components; 1) Facebook groups to provide education and emotional

support to FCGs, 2) web-conferencing to involve FCGs in care plan meetings and, 3) a structured SDM process to guide team discussion. These components will facilitate SDM between the hospice staff and FCGs, lower FCG anxiety, and increase FCG knowledge regarding patient pain, resulting in less pain for cancer patients. A pragmatic cluster randomized controlled trial (PC-RCT) will randomly assign hospice sites to one of three groups: FCG participants at Group 1 sites receive only enhanced usual care (EUC), FCG participants at Group 2 sites receive EUC and participate in Facebook (FB) groups for informational and emotional support, FCG participants at Group 3 sites receive EUC, participate in Facebook groups and the interdisciplinary team meeting for SDM (FB/SDM). Usual hospice care will be enhanced through education on SDM for all staff.

This study will last five years. Participants will be in the study for up to 120 days, depending on the death or discharge of their patient. Team meetings are held every other week, Facebook groups will be visited at least two times per week. Data collection will be done on the following schedule: baseline (day one), day 14, day 30, day 60, day 90, and on or before day 120. Data collection may end earlier at 14-21 days after the death or termination of the patient from hospice services or if a study volunteer chooses to end their participation. A qualitative interview will be done on or around the same day that the last quantitative measures are gathered.

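### Hospices are randomised and cross over, but the analysis section assumes individual allocation and the H1/H2 model has no hospice or period term, so its intervals are too narrow if outcomes correlate within hospice-periods

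*Combined protocol and SAP*

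**What the plan says.** The document describes the allocation in three ways.

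- **Cluster crossover.** The Abstract states "A CCXOPRCT design initially randomly assigns hospice sites to two of three groups" and "Each cluster will go through two arms of the intervention, although participants will only complete one arm". After a washout each site moves to its second arm, and later returns to its first. The Randomization section names six sites, gives precision as the reason for crossing over, and defends site-level assignment partly because "individuals would not be given random interventions in real life".
- **Parallel cluster.** Study Procedures says the trial "will randomly assign hospice sites to one of three groups".
- **Individual, stratified.** Statistical Analysis expects balance "Because individuals are randomly allocated and the sample size is relatively large", and continues: "Because randomization will be stratified by hospice, equivalent proportions from each hospice will be allocated to each group".

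In Statistical Analysis H1- H3, the printed equation regresses the last post-baseline measure on study group, baseline measure and time since enrolment. The text around it describes a mixed model for slopes, with repeated measures nested in participants and no higher level. Hospice is used once, to see whether the effect differs between sites: "This will be tested by introducing a Study Group X Hospice interaction term into each of the regression models discussed below". Any other term depends on a baseline comparison: "Additional confounders will only be introduced as covariates if we find evidence of imbalance between groups at baseline". No model names period or calendar time.

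**The concern.** Caregivers in one hospice during one period share staff and team meetings. In two of the arms they also share a Facebook group set up for that hospice (Intervention). Some residual correlation within hospice-periods is therefore plausible. An analysis that treats caregivers as independently allocated counts each of them as a full unit of information about the arm contrast, although arm varies only between hospice-periods. The result would be intervals that are too short and tests that reject too often for H1 and H2, including the primary outcome GAD-7. Leaving hospice out also gives up the within-site comparison for which the crossover was chosen.

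The group-by-hospice check does not repair this. It addresses heterogeneity of effect, adds neither period nor hospice-period variance, and has empty cells because no hospice receives all three arms.

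**Working it through.** **Inputs from the document:** six hospices (Randomization); two arms per hospice in the order first-second-first (Abstract); 95% intervals (Statistical Analysis); 642 planned caregiver interviews (Qualitative Data). No power calculation, ICC or period size is given, so there is no sample-size figure to reproduce.

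**Assumptions:** N = 642, with N = 400 as an alternative; residual ICC (after baseline adjustment) from 0.005 to 0.05; 18 equal hospice-periods; each ordered pair of arms used once (ABA, BAB, ACA, CAC, BCB, CBC). The Abstract says a schedule exists but does not show it.

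**Step 1: do hospice effects cancel?** Each arm fills 6 of the 18 cells. In the A-versus-B contrast an A cell has weight +1/6 and a B cell -1/6. The net weights by hospice, in sixths, are 1, -1, 2, 1, -2, -1, with sum of squares (1+1+4+1+4+1)/36 = 12/36. Twelve independent cells also give 12 × 1/36 = 12/36. The hospice component therefore inflates the variance just as hospice-period noise does, and the result does not depend on how stable hospice effects are over time.

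**Step 2: variance ratio.** With total residual variance 1, the true variance is ICC × 12/36 + (1 - ICC) × 6/N. The naive variance is 2/(N/3) = 6/N. The ratio is (1 - ICC) + ICC × N/18. For N = 642 and ICC 0.02 this is 0.98 + 0.02 × 35.67 = 1.693.

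**Step 3: actual error of a nominal 5% test** = 2 × (1 - Φ(1.96/√ratio)).

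| ICC | Ratio, N=642 | Error | Ratio, N=400 | Error |
|---|---|---|---|---|
| 0.005 | 1.173 | 7.0% | 1.106 | 6.2% |
| 0.01 | 1.347 | 9.1% | 1.212 | 7.5% |
| 0.02 | 1.693 | 13.2% | 1.424 | 10.1% |
| 0.05 | 2.733 | 23.6% | 2.061 | 17.2% |

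With 642, error passes 6% at ICC 0.0025 and reaches about 10% near ICC 0.012. Simulating the printed regression agrees: coverage of the 95% interval was about 86-87% at ICC 0.02 and 75-76% at 0.05.

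**Step 4: the parallel reading** (two hospices per arm). The ratio is 1 + (N/6 - 1) × ICC. For N = 642 it is 1.530, 2.060, 3.120 and 6.300 at the same four ICCs, so the error is 11.3%, 17.2%, 26.7% and 43.5%. For N = 400 the error is 8.9%, 12.8%, 19.8% and 34.4%. A valid analysis would have 3 df.

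**Step 5: other crossover schedules.** I took all 219 combinations in which each arm appears in at least three hospices, with hospice autocorrelation 0.8 and 1. The smallest ratio for a pairwise contrast is 1.014 (N = 400, ICC 0.005). At N = 642 and ICC 0.01, error ranges from 5.6% to 13.3%.

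**Step 6: what is not affected.** In simulation (N = 642, ICC 0.01-0.05) the H3 interaction test rejects 4.6-5.9%. The variance ratio for group-by-time slopes is 0.998-1.000. These change only if slopes vary by hospice-period. H3 rises to about 9% if the baseline slope has variance 0.01 between hospice-periods. The time-slope test rises to 5.3-7.6% if 1-5% of slope variance lies there.

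**Step 7: the group-by-hospice check.** Six hospices with two arms each fill 12 of 18 cells, so 6 are empty by design.

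**The case against.** - **The target may not be the primary analysis.** The prose under H1-H3 speaks of longitudinal profiles and slopes, which Step 6 shows are largely unaffected. This stands as a limit on scope. However, the Statistical Analysis section commits H1-H4 to the last available measure and the printed equation does the same, so the affected analysis is at least one of two that are planned.
- **The equation is shorthand.** It shows no subscripts, error term or participant effect, so the absence of a hospice term there is weak evidence. That is fair, but the prose names nesting within participants only, and no model names period.
- **Independence will be checked, and the interaction model would normally carry hospice main effects.** Both are true. The residual check names no remedy. The interaction model is a heterogeneity test and would still lack period and hospice-period variance.
- **A crossover cancels hospice effects.** In a complete two-arm crossover with fully stable hospice effects it does, and naive intervals would even be slightly wide. Here each hospice omits one arm and repeats another. One edge case remains: if H1 pools the two intervention arms and hospice effects are perfectly stable, the ratio falls to about 0.99 in 2 of the 219 schedules at ICC 0.01.
- **The magnitude rests on assumptions, and the parallel wording looks like text left from before the crossover.** Both points stand. A two-period layout gives ratios of 1.52-2.06 at ICC 0.02, depending on autocorrelation. The parallel figures show only why the two descriptions must be reconciled.

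**Conclusion.** The concern holds. Whatever the ICC, the allocation described in Statistical Analysis contradicts the Abstract and the Randomization section, and the H1/H2 model lacks the terms that the crossover requires. The size is conditional. With residual ICC 0.005-0.05 and the assumed balanced schedule, a nominal 5% test of an H1/H2 arm contrast has a real error of 7.0-23.6% with 642 caregivers, or 6.2-17.2% with 400. It is near nominal if the residual ICC is close to zero. The direction was the same for every pairwise contrast in all schedules examined. The conclusion covers the last-observation H1/H2 contrasts. It does not extend to H3 or to within-caregiver slopes unless those slopes vary by hospice.

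**What to change.** 1. In Statistical Analysis, replace the sentences on individual allocation and stratification with the cluster-crossover allocation, and drop the claim that sample size secures balance. Reconcile the one-arm-per-site wording in Study Procedures with the Abstract.
2. For H1/H2, always include hospice and period, and account for hospice-period variation with a small-sample correction. Use either a caregiver-level mixed model with a random hospice-period effect or an analysis of adjusted hospice-period means; the two are similar but not identical when cells are unequal. Choose the estimator, and fixed or random hospice effects, in advance.
3. Do not let hospice or period depend on the baseline significance tests, which also ignore clustering.
4. Limit the group-by-hospice check to the two arms each hospice received.
5. State whether the last-observation or the slope analysis is primary. If it is the slope, say how hospice-level slope variation is handled.

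No new data are needed. The cost is precision. With fixed hospice effects the assumed layout leaves 18 - 10 = 8 df (6 hospice, 2 period and 2 arm parameters). Intervals are then 1.40-1.96 times the naive width over ICC 0-0.05, and 1.44 times at ICC 0. With 642 caregivers the naive half-width is 1.96 × √(2/214) = 0.19 residual SD, and it becomes 0.27-0.37. With random hospice effects the multiple is 1.18-1.78, a best case because the variance components are taken as known.

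In simulation over ICC 0-0.05, the fixed-hospice mixed model with 8 df rejected 1.1-4.7%, which is conservative. Unweighted adjusted means rejected 3.1-6.5%, unevenly between contrasts when cells were unequal. The printed equation rejected 6.7-27.1% at ICC 0.01 or more. As no power calculation is documented, the loss of power should be assessed when the estimator is chosen.
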